Our objectives are to evaluate the effectiveness of “nudges” to clinicians, to patients, or to both in increasing in TUTS referral and engagement; and to explore clinician, patient, inner setting (e.g., clinic), and outer setting (e.g., payment structures) mechanisms related to TUTS referral and engagement. We will employ rapid-cycle approaches to optimize the framing of nudges to clinicians and patients prior to initiating the trial and mixed methods to explore contextual factors and mechanisms.

We will conduct this study with at least 100 clinicians and at least 900 smokers across Penn Medicine’s ACC (the clinician sample size may increase with additional clinicians joining Penn and the patient sample size may be higher given the pragmatic design and delay between determination of eligibility [i.e., patient smokes] and nudge delivery at a subsequent visit). We

expect the study to yield essential insights into the effectiveness of nudges as an implementation strategy to speed the uptake of high value evidence-based TUT within cancer care, and to advance our understanding of the multilevel contextual factors that drive response to these strategies. These results will lay the foundation for how cancer care settings can ensure that patients with cancer who smoke are engaged with evidence-based TUT and may lead to a future R01 focused on scaling-up this approach across other cancer centers involved in the C3I.

OBJECTIVES

Aim 1: Conduct a four-arm pragmatic cluster RCT to test the effectiveness of nudges to clinicians, nudges to patients, or nudges to both in increasing TUTS referral and engagement in cancer patients who smoke, vs. usual care (UC). H1a: Each of the implementation strategy arms will significantly increase TUTS referral and engagement compared to UC. H1b: The combination of nudges to clinicians and to patients will be the most effective.

Aim 2: Conduct a quantitative evaluation using secondary data (obtained via EMR, for patients, and by survey, for clinicians) to identify moderators of implementation effects on TUTS referral and engagement. H2: Nudge impact will be moderated by clinician, patient, and inner setting factors. [Note: the clinician survey will be conducted within a separate study funded by this grant and submitted for IRB approval as a separate protocol; data across the studies will be linked by clinician name and study ID.)

Primary outcome variables:

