4. Early Withdrawal of Subjects:

We are requesting a waiver of informed consent, so the option to early withdraw from this study is not applicable for Aims 1 and 2 of this project.

5. Vulnerable Populations:

Children, pregnant women, fetuses, neonates, or prisoners are not being targeted in this research study.

6. Populations vulnerable to undue influence or coercion:

We will not be targeting participants who are likely to be vulnerable to undue influence or coercion. Clinicians employed by Penn may experience undue influence to take part in this study and, as outlined in <https://irb.upenn.edu/sites/default/files/IRB%20SOP%20V.11.1-06.2019-Clean.pdf>, efforts are needed to prevent against this potential. To this end, we will send a formal general notification to all clinicians regarding the proposed study, indicating that it will involve data ascertainment from the EHR, that they can opt out, and that decision to opt out will be confidential.

STUDY DESIGN

Aim 1. We will test optimized implementation strategies in a four-arm pragmatic cluster pilot RCT to test the effectiveness of nudges to clinicians, nudges to patients, or nudges to both in increasing TUTS referral and engagement in cancer patients who smoke, vs. usual care (UC – default referral only). Primary and secondary implementation and effectiveness outcomes, and contextual factors that shape implementation effectiveness, will be captured.

Aim 2. We will explore moderators of effectiveness by analyzing associations with variables available via the EMR and clinician survey.

Study Duration:

The exposure period will be 6 months for all participants, with a 90-day follow-up period to measure persistence of effects after implementation strategies end. The baseline period will be 3 months in length, permitting use of rapid cycle approaches (RCA; meetings with co-investigators [name] and [name] and administrators and clinicians within the

Implementation Lab to refine nudges) during this period to optimize implementation strategies. Study analyses will proceed after the follow-up period has completed.

METHODS

1. Study Measures:

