The Aim 1 primary measure of implementation is penetration (TUTS referral rate), defined as the number of TUTS orders signed, divided by the total number of pended orders (i.e., 1-cancellation rate). Our secondary measures of implementation include: prescription rate, defined as the number of pended orders accompanied by a signed prescription order for any of the seven FDA-approved medications for tobacco cessation, divided by the total number of pended orders; treatment engagement rates (medication), defined as the number of patients who make a pharmacologically-assisted quit attempt using any of the seven pharmacotherapies within 90 days of the initial oncology visit, divided by the total number of referred patients; treatment engagement rate (behavioral), defined as the number of patients who receive a quit-line referral or in-person or telephone cessation counseling, divided by the total number of TUTS-engaged patients; quit attempt rate, defined as the number of TUTS-referred patients who make any quit attempt, divided by the total number of TUTS-referred patients; and abstinence rate, defined as the total number of TUTS-referred patients self-reporting 7-day point prevalence abstinence at a 90-day follow-up assessment, divided by the total number of TUTS-referred patients. Established guidelines state that real-world pragmatic, population-based trials such as this do not require biochemical verification of abstinence and including it could introduce significant bias.⁴² Note, we will continue to monitor assessment rate (defined as the number of times the BPA is answered divided by the total number of times it fires) to ensure the intervention does not negatively impact assessment of tobacco use status by staff collecting vital signs or initially rooming the patients such as nurses, front desk staff, MAs, nursing assistants or technicians(baseline rate=90%).

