6. Statistical Analysis:

Based on our preliminary data, we anticipate including at least 900 smoking patients (based on prevalence estimate of ~7% among 13,000 patients screened over a 1-year study period), nested within at least 100 clinicians. Analysis will use the first TUTS order generated for each patient/physician combination. Data are clustered within clinician, and the exchangeable correlation observed from other studies is small (0.07). We calculated power requirements by simulation using Stata 15, assuming a logistic regression model fitted using generalized estimating equations (GEE), and found our sample gives us 80% power to detect 11% improvement in our primary outcome (e.g., from current 34% referral rate to 45%), using a two-sided type 1 error rate of 5%, for planned comparisons between usual care and each individual nudge arm. The effect of the combined nudge arm is expected to be larger than each individually, indicating at least 80% power to detect probable effects for the comparison between usual care and the combined arm.

We have defined our intention to treat (ITT) sample using the coding algorithm that makes intervention possible, irrespective of whether a nudge was delivered or received. Thus, the ITT cohort is comprised of all eligible patients, defined as those who screened positive for tobacco exposure and have completed the two visits in their randomly assigned cluster. Eligible patients may or may not receive the nudge to which they were assigned and may or may not have access to MyPennMedicine; regardless, all eligible patients are analyzed in the ITT sample.

We have patient-level data on all those screened positive for tobacco but who did not complete the subsequent visits with a clinician in our cluster randomization (e.g., patient came for the first visit where the hidden system variable was assigned and never returned). While these patients are not considered eligible for our trial, they are part of the “screened” population, and we can compare them to our eligible patients on available data to assess the generalizability of our sample.

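### Four secondary rates are divided by patients selected after randomisation (referred, or an undefined TUTS-engaged group), so their arm comparisons are not randomised ones and the two engagement rates do not test H1a's engagement claim

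*Combined protocol and SAP*

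**What the plan says.** METHODS, 1. Study Measures, lists four secondary measures whose denominators depend on events after randomisation:

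- Medication engagement: patients with a medication-assisted quit attempt "using any of the seven pharmacotherapies within 90 days of the initial oncology visit, divided by the total number of referred patients".
- Behavioural engagement: the "number of patients who receive a quit-line referral or in-person or telephone cessation counseling, divided by the total number of TUTS-engaged patients". The last term is not defined in the document.
- The "quit attempt rate, defined as the number of TUTS-referred patients who make any quit attempt, divided by the total number of TUTS-referred patients".
- Abstinence: patients "self-reporting 7-day point prevalence abstinence at a 90-day follow-up assessment, divided by the total number of TUTS-referred patients".

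The hypothesis is wider. H1a reads "Each of the implementation strategy arms will significantly increase TUTS referral and engagement compared to UC", and STUDY DESIGN, Aim 1, speaks of "increasing TUTS referral and engagement in cancer patients who smoke".

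The statistical analysis section fits one kind of model, logistic GEE with terms for clinician and patient prompt, to every binary outcome of Aim 1. It defines the intention-to-treat cohort as all eligible patients, "defined as those who screened positive for tobacco exposure and have completed the two visits in their randomly assigned cluster", and says that "regardless, all eligible patients are analyzed in the ITT sample". METHODS, 4. Subject Follow-up, plans the 90-day telephone call for referred patients only.

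**The concern.** Key Eligibility Criteria places the primary outcome, clinician referral, at the visit where the nudge logic is applied. Being referred is therefore a consequence of randomisation. If a nudge works, its referred group contains patients who would not have been referred under usual care, and the usual-care referred group contains no such patients. Comparing the two groups mixes any effect on engagement or quitting with a change in who is counted.

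Two things are at stake. First, half of H1a concerns engagement. A nudge that brings more smokers into treatment can lower the rate per referred patient, so the planned measure can point the opposite way to the hypothesis. Second, for quit attempts and abstinence, which H1a does not name, a difference between arms can appear when no patient's outcome changed, and a real difference can be hidden.

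**Working it through.** **The plan's own figures.** The plan gives no rate or power for these four outcomes, so there is nothing to reproduce. Its 80% power statement concerns the primary outcome and is not used here.

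**Inputs from the plan (Statistical Analysis).** Referral 34% in usual care and 45% with a nudge; 900 patients; 100 clinicians; exchangeable correlation 0.07; two-sided 5%.

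**Assumptions.** Equal allocation (225 patients and 25 clinicians per arm); equal cluster sizes; one pended order per eligible patient; nudges only add referrals; the 0.07 correlation, given for the primary-outcome power calculation, also applies to abstinence among referred patients. All engagement and abstinence rates are assumed, because the documents give none.

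**Step 1: who is compared.** Referred patients number 225 × 0.34 = 76.5 in usual care and 225 × 0.45 = 101.25 in a nudge arm. The added share is (0.45 − 0.34)/0.45 = 24.4%.

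**Step 2: engagement.** Take 30% engagement in always-referred patients. Added patients engage at 15% if referred and 5% if not.

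- Per referred: 30.0% in usual care; (0.34 × 0.30 + 0.11 × 0.15)/0.45 = 26.3% with the nudge.
- Per eligible: difference = 0.11 × (0.15 − 0.05) = +1.1 points.

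Engagement rises among eligible patients while the planned rate falls by 3.7 points.

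**Step 3: abstinence with no true effect.** Take 20% in always-referred patients and rate *a* in added patients. The nudge arm's per-referred rate is q = (0.34 × 0.20 + 0.11*a*)/0.45. Design effects are 1 + (76.5/25 − 1) × 0.07 = 1.144 and 1 + (101.25/25 − 1) × 0.07 = 1.214. Then z = (q − 0.20)/√(0.20 × 0.80 × 1.144/76.5 + q(1 − q) × 1.214/101.25).

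| *a* | q | OR vs 20% | z | Rejection at nominal 5% |
|---|---|---|---|---|
| 5% | 16.3% | 0.78 | −0.58 | 8.9% |
| 10% | 17.6% | 0.85 | −0.38 | 6.7% |
| 20% | 20.0% | 1.00 | 0 | 5.0% |
| 30% | 22.4% | 1.16 | 0.37 | 6.5% |

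**Step 4: the planned main-effects model.** I fitted the two prompt terms to the four arms' log-odds, weighting each arm by n·q(1 − q)/design effect. The result depends on how referral varies over usual care / clinician / patient / both. Rejection for the clinician prompt:

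| Referral pattern (%) | *a* = 5% | 10% | 20% | 30% |
|---|---|---|---|---|
| 34/45/45/45 | 6.9% | 5.8% | 5.0% | 5.7% |
| 34/45/45/56 | 10.8% | 7.4% | 5.0% | 7.0% |
| 34/45/34/45 | 13.0% | 8.4% | 5.0% | 8.1% |

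In the first two patterns the patient prompt gives the same values. In the third the patient prompt is inert and stays at 5.0%.

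**Step 5: what bounds would show.** Suppose both arms report 20% abstinence per referred patient. With 24.4% of the nudge group being added patients, the always-referred rate in that arm lies between max(0, (0.20 − 0.244)/0.756) = 0% and 0.20/0.756 = 26.5%. The difference from usual care lies between −20.0 and +6.5 points.

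**Step 6: *TUTS-engaged*.** If it means having received counselling or a quit-line referral, numerator and denominator nearly coincide and the rate is close to 100% in every arm. If it means referred, or reached or enrolled by TUTS, the rate can vary, but the denominator is still selected after randomisation.

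**The case against.** The best defence has four parts.

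- Per-referred rates are ordinary cascade measures, and these are secondary measures in a trial that the protocol calls a pilot. That stands for description. The testing hierarchy does not name these outcomes, so a reader who infers that they were meant as confirmatory tests goes beyond the text. But the plan still models them by prompt, and engagement is part of H1a.
- The intention-to-treat paragraph may already cover them. A reader might infer the reverse, that it flatly contradicts Study Measures. Neither follows. The sentence deals with whether the nudge was received and whether the patient had portal access. It does not restate these denominators, so the two sections need reconciling.
- No bias has been demonstrated. That is correct: the outcome rates above are assumed, and if added and always-referred patients have equal rates the bias is zero. The plan gives no basis for assuming that they are equal.
- Moving to all eligible patients could create a new bias. This also stands. If events are recorded more completely for referred patients, scoring an absent record as 0 makes extra referral look like extra engagement. The fix has to require equal capture.

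**Conclusion.** The point holds for four outcomes. Their denominators arise after randomisation, one is undefined, and neither engagement rate measures engagement among smokers with cancer, as H1a and Aim 1 require. The reversal in Step 2 shows what can go wrong under the plan's own referral rates and assumed engagement rates; it is not a prediction.

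For abstinence, the error inflation is modest at a 20% base rate: at most 8.9% for one arm against usual care, and at most 6.9%, 10.8% or 13.0% for a prompt main effect, depending on the referral pattern. The 13.0% needs one prompt to do nothing to referral and should not be read as the general case. Direction is unknown, since the sign changes with the added patients' rate.

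Two further inferences are not supported. The behavioural rate is near 100% by construction under only one reading of *TUTS-engaged*. And the primary outcome and the prescription rate, both per pended order, are not touched by this point.

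**What to change.** **(a) Engagement, for H1a.** Define it over all eligible patients in the intention-to-treat cohort, as counselling or quit-line referral and as medication prescribed. Use only sources that capture the event equally for referred and non-referred patients, and count no recorded event as 0 in those sources only. Label prescription data *medication prescribed*, not a quit attempt. For counselling delivered through TUTS, name the outcome *TUTS engagement recorded*, so that 0 for a non-referred patient is true by definition. Amend Study Measures and the intention-to-treat paragraph so that they agree.

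**(b) Telephone outcomes.** Quit attempts, abstinence and telephone-reported medication use are collected only from referred patients. Report them per referred patient by arm as descriptive, or state that any arm comparison is non-randomised and add bounds as in Step 5. Do not score non-referred patients as 0.

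**(c)** Remove *TUTS-engaged* as a denominator. Leave the primary outcome and the prescription rate as they are.

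**Cost.** Text changes in two sections, and a check of what the EMR and TUTS databases hold for non-referred patients. Per-eligible rates will be lower, and the telephone outcomes lose a modelled arm comparison. Keeping a comparison of quitting free of selection by referral would mean calling all eligible patients. That is about 495 more calls with referral of 34/45/45/56 (900 − 225 × 1.80) and up to 594 with 34% in every arm (900 − 306), a larger change than is asked for here. Selection by attendance remains in any case, because eligibility itself requires the later visits.

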- 2) Prescribing authority in Pennsylvania (i.e., physician, nurse practitioner, physician assistant)
- 3) Cared for at least 1 tobacco-using patient in 30 days prior to recruitment
- 4) English-speaking (messages will be in English)

Patient participants must be diagnosed with cancer and report current tobacco smoking (as assessed by any staff collecting vital signs or initially rooming the patients such as nurses, front desk staff, MAs, nursing assistants or technicians during an Index Visit). Patients are considered in the analyzable dataset after their Index Visit and after they have a clinic visit with a clinician in the study at which point a nudge may have been delivered (see steps below).

The process by which patients become eligible for inclusion involves a 3-step algorithm employed in the EMR:

- Step 1 – All patients seeking care within the participating Abramson Cancer Center programs are screened for tobacco use status in order to ascertain relevance to the project (i.e., tobacco exposure). This screening encounter need not be a visit with a clinician who is in the cluster randomization.
- Step 2 – This step occurs at the first visit with a clinician within the cluster randomization. Note that this might be the same encounter in which screening occurs, but does not have to be. At this visit, all patients identified as current smokers are assigned a hidden (i.e., system) variable, the value of which is based on the clinician they are scheduled to meet during that visit (i.e., cluster membership).
- Step 3 – The logic is engaged at the next (third in series) visit, wherein the system variable is used to guide the intervention based on the clinician's cohort. There must be this visit to permit the delivery of the nudges (or not, if in usual care arm). The primary outcome is clinician referral for tobacco cessation through the EHR at this visit. Thus, patients eligible for this study are only those who are screened (and positive for tobacco use) and have completed the two visits in their randomly assigned cluster (clinician clusters are the unit of randomization) during the study period.

3. Subject Recruitment and Screening:

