This is a pragmatic clinical trial focused on increasing use of TUTS. In all arms, clinicians can still choose what they like and patients can still decide to engage in TUTS or not. We will seek a waiver of informed consent for clinicians and patients. We will identify clinicians at the practice sites and their patients using the EMR. Patients will be required to meet the above outlined eligibility criteria. Clinicians (i.e., the unit of randomization) within each site will be randomized to four arms using variable permuted blocks. To control for confounding due to the fact that a small number of clinicians may potentially treat patients at multiple sites, clinicians will be randomized to arm irrespective of site.

We will use RCA to optimize implementation strategies to ensure face validity and maximum effect. We will focus on optimizing content, messaging, and design. RCA procedures involve design meetings with [name] and [name] and with discussions with administrators and clinicians who are members of our Implementation Lab. Clinicians and patients will be exposed to implementation strategies based on their assigned arm.

2. Study Intervention Phase:

Nudges to Clinicians. We will use the Best Practice Alert functionality within the EMR as our conduit to the point of decision-making. All sites use Epic (Epic Systems Corporation, Verona,

WI) to deliver care, or an interoperable system. Epic BPA deployment is modifiable, as we have done at the ACC (CA016520-41S4) and in primary care (DA045244). Epic currently “fires” a BPA for each new patient presenting to ACC within the check-in and vital sign workflow, requiring that staff collecting vital signs or initially rooming the patients such as nurses, front desk staff, Mas, nursing assistants or technicians assess tobacco use status within the past 30 days and satisfy the alert with one of three possible answers (CA016520-41S4). They then activate the “Order” tab for all patients identified as current smokers (i.e., within the past 30 days), resulting in placement of a pended order for consult to TUTS within the clinical workflow.

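### The assessment-rate check cannot show smokers recorded as non-smokers or smokers left without a pended order, and it is not specified by arm, although both steps feed the primary referral rate

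*Combined protocol and SAP*

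**What the plan says.** METHODS, 1. Study Measures, recognises that the intervention might impair tobacco assessment by rooming staff. Its check is to "monitor assessment rate (defined as the number of times the BPA is answered divided by the total number of times it fires", with a baseline of 90%. It does not say whether the rate is overall or by arm, and gives no threshold, review date or action.

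The same section defines the primary measure as "the number of TUTS orders signed, divided by the total number of pended orders", which it equates with one minus the cancellation rate.

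STUDY PROCEDURES, 2. Study Intervention Phase, says the alert fires "for each new patient presenting to ACC within the check-in and vital sign workflow". Staff must "satisfy the alert with one of three possible answers". For those recorded as current smokers they then activate the order tab, "resulting in placement of a pended order for consult to TUTS within the clinical workflow".

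Under 2. Key Eligibility Criteria, screening is Step 1. Step 2 is the first visit with a randomised clinician and may be the same encounter as screening; there, "all patients identified as current smokers are assigned a hidden (i.e., system) variable". The primary outcome is referral at the following visit, Step 3.

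6. Statistical Analysis defines an ITT cohort of all eligible patients: screened positive, with both visits completed in the assigned cluster. It also says the analysis takes the first TUTS order for each patient and physician pair.

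**The concern.** Three staff actions matter here: answering the alert, recording the patient as a current smoker, and pending the order. The check measures only the first. The second decides who can enter the trial; the third decides who is in the signed/pended denominator.

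Both unmeasured actions can take place after clinicians have been randomised, and blinding of staff is not described. In two of the four arms clinicians meet an overlay that they must acknowledge, or opt out of with a reason. The Background reports individual referral rates from 0% to 100%, so cancellation is concentrated in some clinicians. If staff spared frequent cancellers in those arms, would-be cancellations would leave the denominator and the referral rate would rise with no change in clinician behaviour. The smokers concerned would also miss the default referral, while the reported assessment rate looked unharmed.

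**Working it through.** **Inputs.** Answered/fired 90% (Study Measures). Referral 34%, target 45%, smoking prevalence about 7% of 13,000 screened a year (Statistical Analysis). Prevalence under 10% (Background).

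**1. The plan's own figures.** 0.07 × 13,000 = 910, which agrees with the planned 900. With rate = 1 − cancellation, 34% signed means 66 of every 100 pended orders are cancelled.

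**2. What the check sees within an affected arm.** Suppose a share of smokers is lost while the alert is still answered.

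| Route of loss (10% / 20% / 24.4%) | Answered/fired | Smoker/answered | Pended/smoker |
|---|---|---|---|
| Smoker recorded as non-smoker | 90% throughout | 7% × (1 − loss) = 6.3% / 5.6% / 5.3% | unchanged |
| Smoker recorded, order not pended | 90% throughout | 7% throughout | down by 10% / 20% / 24.4% of its baseline |

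Splitting answered/fired by arm would therefore not reveal either route. Two further ratios are needed, one for each.

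**3. Skipped alerts are different.** If a share f of smokers' alerts goes unanswered, and answering is otherwise unrelated to smoking (assumption), the affected arm reads 90% × (1 − 0.07f). For f = 25%, 50%, 100% this is 88.4%, 86.9%, 83.7%. With two of four equal arms affected, the overall figure is 89.2%, 88.4%, 86.9%. The check does move, though modestly, and no threshold is set.

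**4. Effect on signed/pended, worst case.** Assume no true effect and that all L lost orders per 100 would have been cancelled. Rate = 34/(100 − L).

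| L | Share of would-be cancellations, L/66 | Signed/pended | Bias (points) |
|---|---|---|---|
| 10 | 15.2% | 34/90 = 37.8% | +3.8 |
| 20 | 30.3% | 34/80 = 42.5% | +8.5 |
| 24.4 | 37.0% | 34/75.6 = 45.0% | +11.0 |

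The last row solves 34/(100 − L) = 0.45, so L = 100 − 34/0.45 = 24.4.

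**5. Less selective loss.** If a share s of the lost orders would have been cancelled, rate = [34 − L(1 − s)]/(100 − L). At L = 20:
- s = 0.90 gives 32/80 = 40.0%;
- s = 0.80 gives 30/80 = 37.5%;
- s = 0.66, meaning loss unrelated to cancellation, gives 27.2/80 = 34.0% and no bias.

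**6. Per eligible patient.** Take 100 eligible patients, with no order counted as not referred. Non-pending of would-be cancellations leaves 34/100 = 34% for every L. Unselective non-pending of 20 gives 34 × 0.8 = 27.2%, a true fall in referral. Misrecorded smokers leave this cohort too, so step 4 still applies to them.

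**7. Precision of smoker yield by arm.** If 13,000 screenings split equally over four arms (3,250 each, an assumption), the standard error of a two-arm difference is √(2 × 0.07 × 0.93/3,250) = 0.63 points before clustering. A fall from 7% to 5.6% is 2.2 standard errors; a fall to 6.3% is 1.1. Six months of exposure gives fewer screenings, so yield is a descriptive signal.

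**The case against.** The route from arm to staff behaviour is indirect. The alert fires for new patients, screening may precede any contact with a randomised clinician, the arm variable is hidden, and the overlay appears to the clinician at a later visit. Staff would have to know a clinician's arm and act to spare a future alert. The Background reports screening steady at about 90% while clinicians cancelled most orders. The ITT cohort is defined by eligible patients, which would count an unpended order as a non-referral, and the DSMB reviews data quality and accrual.

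Much of this stands, and it makes the mechanism possible rather than likely. It does not close the gap. The steady 90% appears to be the same answered/fired rate, which cannot show the loss in question. The Study Measures section still defines the primary rate per pended order, and the Statistical Analysis section refers to first orders without saying that an eligible patient with no order counts as not referred. The planned comparison with screened-positive patients who did not complete the visits concerns generalisability and omits anyone misrecorded. DSMB meetings fall every six months, the length of the exposure period, and no by-arm screening review is named.

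A reader might infer more than the text supports:
- That the rate is pooled over arms. The plan is silent on this.
- That it stays at 90% whatever staff do. Skipped alerts lower it (step 3).
- That some clinics are nudge clinics. Clinicians are randomised irrespective of site.
- That the trial's result will be inflated. That needs loss that is both arm-related and selective, and no such behaviour is reported.

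**Conclusion.** The point holds as a gap in monitoring and in the choice of denominator. Answered/fired is the only screening-specific check described, and by construction it is blind to misrecorded smokers and unpended orders. Whether bias would follow is unknown. The 3.8, 8.5 and 11.0 points are worst-case figures that assume no true effect, a 34% baseline and loss made up entirely of would-be cancellations. Reaching 45% requires removing 37% of those and no would-be referrals. Partial selectivity gives less, and unselective loss gives none. Non-pending inflates only the signed/pended rate; misrecording can inflate either denominator.

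**What to change.** 1. Keep answered/fired and add two rates: current smokers per answered alert, and pended orders per recorded smoker. Report all three by arm of the scheduled or Step 2 clinician, against the 3-month baseline period. Show encounters with no randomised clinician separately, since they have no arm. State who reviews the rates and when.

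2. Analyse the primary outcome per eligible patient in the ITT cohort, counting no pended or signed order at the Step 3 visit as not referred. Make this the primary analysis or a prespecified sensitivity analysis, so that non-pending cannot raise the rate. The denominator should not be widened to every screened-positive patient, because the Statistical Analysis section makes those who did not complete the visits ineligible.

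The second change cannot recover smokers recorded as non-smokers; only smoker yield by arm would reveal them, within the precision shown in step 7.

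The cost is a few extra counts from EMR data already held, the work of linking encounters to a clinician's arm, and one extra analysis. Arm-level process data should be handled outside the nudge design team.
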